IRB Application for Population Health and Quality Research Study

Title of Study: Combined administration of Bupivacaine and Exparel versus Bupivacaine or Exparel alone for postoperative analgesia in posterior lumbar spine surgery - A Prospective Randomized Study

Background and Statement of Context

It is estimated that 1 million elective (inpatient and outpatient) spinal surgery procedures are performed each year in the US, including 464,000 spinal fusions, 342,000 discectomies, and 213,000 laminectomies [1, 2]. Spine surgery is thought to result in severe postsurgical pain for a variety of reasons, including the size of the incision, the damage that may occur to ligaments, muscles, bone, discs, and joints when performing the surgical procedure, the existence of preoperative pain, and opioid-induced hyperalgesia (OIH) that may occur with pre-operative opioid use [3]. OIH may result in sensitization of the dorsal horn of the spinal cord where pain signals are first processed, reducing the threshold required to perceive pain, thereby prolonging and magnifying its effect [4]. Pain following spine surgery is thought to be most intense after a few hours, gradually subsiding over a few days, as supported by pain severity scores recorded in studies of various approaches to managing postsurgical pain [5]. Uncontrolled postsurgical pain results in delayed mobilization and consequently longer length of hospital stay (LOS) and morbidity associated with bed rest, increased opioid usage, and lower patient satisfaction.

A variety of approaches are currently used to manage postsurgical pain, including pre-emptive analgesia, systemic analgesia, regional analgesia, and local analgesia [6]. These approaches are often combined in a multimodal regimen intended to address the various components of postsurgical pain, including nociceptive, neuropathic, and inflammatory mechanisms [7]. Many of the current approaches to managing postsurgical pain require use of opioid analgesics such as morphine, fentanyl, hydromorphone, hydrocodone, or oxycodone [8]. Many of these approaches provide only temporary pain control since the medications used have a short duration of effectiveness [9, 10]. Repeated or continuous dosing is therefore necessary to extend their effectiveness, which must be administered by clinical staff (e.g. IV or IM bolus), Patient Controlled Analgesia (PCA) device, elastomeric pump, or taken orally when permitted (e.g. after regaining gastrointestinal motility).

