- 5. Reduced time to achieve physical therapy discharge criteria (criteria set according to each patient's living situation, preoperative physical function, comorbidities, and other goals)
- 6. Reduced inpatient length of stay (LOS)

Study Benefits to Virtua

This study could potentially benefit Virtua in several ways. If Exparel is shown to reduce postoperative pain for spine surgery patients, and consequently reduce their opioid consumption for postoperative pain management, then there could be the potential to see an improvement in patient satisfaction with regards to pain management. In addition, Virtua could stand to gain some cost savings if Exparel is shown to support decreased incidence of ORAEs such as respiratory depression, leading to reduced time to physical therapy discharge criteria and consequently reduced LOS.

If on the other hand, the study indicates that the more expensive Exparel is no more effective at managing postoperative pain compared to the cheaper alternatives, then Virtua stands to directly gain significant cost savings by adopting the use of the cheaper options as standard practice.

Study Methodology

Patients who meet all of the following inclusion criteria may be eligible to participate in the study if:

- 1. Age 18 or older;
- 2. Primary indication is low back pain, lumbosacral radiculopathy, lumbar disc degeneration, lumbar disc herniation, stenosis, spondylolisthesis, spondylolysis, or deformity requiring surgical intervention;
- 3. Scheduled to undergo primary, 1 or 2 level, posterior lumbar laminectomy with or without fusion, discectomy with fusion, or fusion at Virtua Memorial Hospital;
- 4. Willing to provide informed consent, participate in study, and comply with study protocol.

Patients who meet any of the following criteria may not be eligible to participate:

- 1. Hypersensitivity or allergy to local anesthetics;
- 2. Pregnant or contemplating pregnancy prior to surgery;
- 3. Previous surgery in lumbar spine (i.e. other than microdiscectomy);
- 4. Prior treatment for alcohol, recreational drug, or opioid abuse;
- 5. Serious spinal conditions (e.g. spinal cord compression, cauda equina syndrome, spinal infection, spinal tumor, spinal fracture, inflammatory or systemic spinal arthritis);
- 6. Surgery involving more than 2 vertebral levels;

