On the day of surgery, in the operating room, the circulating nurse will roll a die to randomly assign the patient to one of the three pain management groups. The study intervention group (die roll outcome 1 or 2) will receive a local infiltration of EXPAREL and bupivacaine 0.5% w/v solution into the surgical site (1 level patients – 20 mL Exparel + 30 mL bupivacaine 0.5% w/v solution; 2 level patients – 20 mL Exparel diluted to 40mL + 30 mL bupivacaine 0.5% w/v solution). The two medications will not be combined in the same syringe to minimize the possibility of a direct interaction between the two. While to date, no such interaction has been confirmed, we will maintain a strict "no mixing of bupivacaine and Exparel in the same syringe" policy throughout this study. The second group (die roll outcome 3 or 4) will only be administered local infiltration of Exparel (1 level patients – 20 mL Exparel; 2 level patients – 20 mL Exparel diluted to 40 mL). The third group will be treated to a local infiltration of 30 mL bupivacaine 0.5% w/v solution. Anesthesiologists will use their usual pre-operative and intra-operative techniques for all study participants and both study groups will receive nurse-administered rescue opioids as needed.

The patients and all staff, including hospital nursing staff, case management, and physical therapists, will be blinded as to which pain management treatment the patient received. While the surgical team cannot be blinded because the appearance of the drugs is different, they will however, not be assessing the outcome measures.

The primary outcome in this study will be the mean postoperative pain score derived from the pain scores recorded by the nursing staff in each participant's clinical records using the visual analog scale of 0-no pain to 10-extreme pain, several times in each 24-hour period, for the entire duration of the patient's hospital stay. Adopting [20] assumptions of a target reduction in mean overall postoperative pain scores of 1 point on the VAS and our anticipated variance of 2, it is estimated using one-way analysis of variance that for a statistical power of 80% and significance level of 0.05, a minimum of 40 participants will be required in each study group for a total of 120 study participants. To minimize the possibility of dropouts or incomplete data impacting the analysis, a minimum of 45 participants will be enrolled in each study group, for a total of 135 enrollees.

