Secondary outcome measures in this study include total opioid consumption. All opioid analgesics used in the hospital will be recorded in the participant's clinical record, including: Name of medication (e.g. morphine); Dose administered (e.g. 10mg); Route of administration (e.g. IV, IM, oral); Reason for administration (e.g. surgical site pain). All opioid analgesics will be converted into oral mg morphine equivalent to determine the total dose of opioids used during the hospital stay using the conversion factors in Appendix 2. Other secondary outcome measures include mean time to achieve physical therapy discharge criteria, mean LOS, and incidence of ORAEs. ORAEs will be documented using the checklist shown in Appendix 3 with assistance from a nurse during every nursing shift (i.e. every 12 hours) until hospital discharge).

Means will be compared among all the three arms using analysis of variance, proportions will be compared using chi-square tests, and logistic regression will be used to analyze for confounding effects. All statistical analyses will be conducted in Minitab 16 Statistical Software.

Protection of Human Subjects

Throughout the study, the principal investigators (Virtua Memorial spine surgeons and PAs), will be the only ones with access to the data collection database. Following the completion of the study, all personal health information collected, including name, gender, age, significant medical comorbidities, and postoperative complications, will be de-identified as soon as possible prior to data analysis and any subsequent publications or research submissions. Patient would be told participation is purely voluntary with no monetary reimbursement and minimal risk of being assigned to one of the three pain management groups.

References

- 1. Centers for Disease Control and Prevention (CDC). National Hospital Discharge Survey: 2006 Annual Summary. Vital and Health Statistics, 2010;13(168).
- 2. Centers for Disease Control and Prevention (CDC), Health, United States, 2012: With Special Features on Emergency Care. 2012: Hyattsville, MD.

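### Logistic regression, the only adjustment method named, cannot adjust the continuous primary outcome; a prespecified linear model on number of levels and planned fusion could gain precision for at most about 1 power point

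*Combined protocol and SAP*

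**What the plan says.** The analysis plan is a short paragraph in Study Methodology. It states: "Means will be compared among all the three arms using analysis of variance"; then "proportions will be compared using chi-square tests"; then "logistic regression will be used to analyze for confounding effects". It names no covariates, does not say which outcomes the logistic regression serves, and mentions no linear regression or analysis of covariance.

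The primary outcome paragraph of the same section says: "The primary outcome in this study will be the mean postoperative pain score". This is a 0–10 score averaged over the hospital stay. The sample size has the same unadjusted basis: "it is estimated using one-way analysis of variance that for a statistical power of 80% and significance level of 0.05", giving 40 per group, with 45 per group to be enrolled.

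Allocation takes place in the operating room, where "the circulating nurse will roll a die to randomly assign the patient to one of the three pain management groups". No stratification is described. Inclusion criterion 3 admits patients "Scheduled to undergo primary, 1 or 2 level, posterior lumbar laminectomy with or without fusion", so the number of levels and whether fusion is planned are known from the schedule before allocation.

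**The concern.** Logistic regression models a categorical outcome. The clause can be read in two ways, and both leave the same gap.

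- **It covers every outcome.** The method then does not fit mean pain, total opioid dose, time to physical therapy criteria or length of stay.
- **It covers only the proportions, because it follows the chi-square clause.** It then suits adverse-event incidence, but no adjustment is planned for any outcome compared as a mean.

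Validity is not at stake. Allocation is random, so the unadjusted ANOVA is unbiased, and its standard error already allows for chance imbalance. What may be lost is precision. The Background lists among the causes of pain after spine surgery "the size of the incision, the damage that may occur to ligaments, muscles, bone, discs, and joints when performing the surgical procedure". It is an inference, not a statement in the documents, that these vary with number of levels and with fusion. If they do, that variation inflates the ANOVA error term and a linear model would remove it.

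There is also a specification risk. The sponsor evidently intends some adjusted analysis, and as written its method and covariates would be chosen later, possibly after the data have been seen.

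**Working it through.** **Inputs from Study Methodology:** target difference 1 point, variance 2, significance level 0.05, power 80%, three groups, 40 per group needed (120), 45 enrolled (135), allocation by die roll.

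**Assumptions, not in the documents:** R² (the share of pain variance explained by levels and fusion together), the prevalence of each factor, and the two factors being independent with equal effects.

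**1. Reproduce the stated sample size.** With means 0, 0.5 and 1, the noncentrality is λ = n·Σ(μᵢ − μ̄)²/σ² = 40 × (0.25 + 0 + 0.25)/2 = 10. The noncentral F with 2 and 117 degrees of freedom gives 80.5% power. At 39 per group it is 79.4%. The plan's 40 is reproduced exactly.

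**2. Add two covariates, by formula.** The residual variance becomes 2(1 − R²) and the error degrees of freedom 120 − 5 = 115. Unstratified allocation also lets the covariates differ between arms by chance, which inflates the variance of the arm comparison by about 1 + 2/(N − 6) = 1 + 2/114 = 1.0175. So λ = 10/[(1 − R²) × 1.0175].

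| R² | λ | Power, imbalance cost included | Power, imbalance cost ignored |
|---|---|---|---|
| 0 | 9.83 | 79.7% | 80.5% |
| 0.02 | 10.03 | 80.6% | 81.3% |
| 0.05 | 10.34 | 81.9% | 82.6% |
| 0.10 | 10.92 | 84.0% | 84.7% |
| 0.20 | 12.28 | 88.2% | 88.8% |

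The third column is the fair comparison with 80.5% unadjusted. The loss at R² = 0 is about 0.75 points, and break-even is at R² of about 0.018 (about 0.016 at 45 per group).

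**3. Simulate with the die roll itself.** Arm sizes vary, so unadjusted power is slightly below the formula. Entries are ANOVA / linear model, with both factors at the same prevalence.

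| R² | N=120, 50/50 | N=120, 20/80 | N=135, 50/50 | N=135, 20/80 |
|---|---|---|---|---|
| 0 | 79.7 / 79.1% | 79.9 / 79.2% | 84.9 / 84.6% | 85.0 / 84.3% |
| 0.02 | 80.0 / 80.0% | 80.1 / 80.2% | not run | not run |
| 0.05 | 79.7 / 81.2% | 80.1 / 81.6% | 85.0 / 86.2% | 84.7 / 86.0% |
| 0.10 | 80.0 / 83.6% | 80.0 / 83.6% | 84.3 / 88.0% | 84.7 / 87.8% |
| 0.20 | 79.8 / 87.5% | 79.7 / 87.5% | 84.9 / 91.3% | 84.5 / 91.5% |

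There were 40,000 trials per cell at N=120 (Monte Carlo standard error about 0.2 points) and 20,000 at N=135. Under the null at N=120, rejection was 5.0–5.1% for the ANOVA and 4.9–5.1% for the linear model, so adjustment does not disturb the type I error.

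**4. What each R² would require.** If each factor shifts mean pain by b and has prevalence p, then 2b²p(1 − p) = 2R², so b = √[R²/(p(1 − p))].

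| R² | b, prevalence 50/50 | b, prevalence 20/80 |
|---|---|---|
| 0.02 | 0.28 points | 0.35 points |
| 0.05 | 0.45 | 0.56 |
| 0.10 | 0.63 | 0.79 |
| 0.20 | 0.89 | 1.12 |

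Beside a treatment target of 1 point, R² = 0.20 is optimistic.

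**The case against.** The case against runs as follows.

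- **No error is shown.** An unadjusted comparison of means is acceptable in a randomised trial, and on the narrower reading of the logistic clause no method is misapplied. This stands, and it is why the point is an improvement and not a fault in the ANOVA or the sample size.
- **The gain is entirely assumed.** R², prevalence and the link from tissue damage to levels and fusion are not in the documents. Rescue opioids given as needed may also compress pain differences between larger and smaller operations. This stands too, and the gain may be near nil. It does not change the balance, because the average loss is under 1 point.
- **Other covariates are named more directly.** The Background also cites preoperative pain and preoperative opioid use. This is fair, and the sponsor may prefer to add one. However, the Appendix 1 pain diagram records site and type, not intensity. Its question on more than 30 days of opioid use sits under exclusion criteria there but not in the main exclusion list, so how far that factor would vary is unclear. Levels and planned fusion are recorded simply and are fixed before allocation.
- **The pattern of means matters.** The hypothesis is that the combination beats both single-drug arms. With means 0/1/1 and 40 per arm, power is 90.8% unadjusted and, with imbalance cost, 91.7%, 93.1% and 95.6% at R² 0.05, 0.10 and 0.20. The gains are smaller but in the same direction. That pattern would need only 30 per arm, so it is not the one behind the plan's 40.
- **Nothing was computed for the secondary outcomes.** Correct. Using the same covariates there is for consistency, and no gain is claimed.

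**Conclusion.** The concern holds. No usable adjustment is planned for the primary outcome or for the other outcomes compared as means. A prespecified linear model on two factors known before allocation is a cheap improvement with a small, known downside.

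At 120 patients the average loss is about 0.7 points if the covariates explain nothing. Break-even is at R² of about 0.02, and the gain is about 1.5 points at R² 0.05, 3.6 at 0.10 and 7.7 at 0.20. These figures rest on assumed R² and prevalence and on the 0/0.5/1 pattern of means. The loss is an average over randomisations, and one badly imbalanced trial could lose more. Adding a levels-by-fusion interaction would raise the worst-case average loss to about 1.1 points. The sponsor should make the change, but the trial does not depend on it.

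**What to change.** 1. Prespecify the primary analysis as a linear model of mean pain on arm, number of levels (1 or 2) and planned fusion (yes or no), with the overall three-arm F test for arm on 2 and N − 5 degrees of freedom.
2. Take both covariates from the scheduled procedure and record them as named data items before the die roll.
3. Report the unadjusted ANOVA alongside.
4. Use the same two covariates for total opioid dose, time to physical therapy criteria and length of stay.
5. State that logistic regression is for the incidence of opioid-related adverse events.

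The cost is a change of wording, two data items, two error degrees of freedom, and at most about 1 power point on average if the covariates explain nothing. No extra patients or visits are needed.

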APPENDIX 1. SCREENING QUESTIONNAIRE

Participant information

Last name	Date of birth	//
First name	Age	

Contact information

Home phone	() -	Cell phone () -
Home street address		
Home city, state, Zip		
Email		

Inclusion criteria

#		Yes	No
1	Are you able to speak, read, and write in English?		
2	Are you able to speak, read, and write in Spanish?		
3	Do you have low back pain, radiculopathy, disc degeneration, disc		
	herniation, stenosis, spondylolisthesis, or mild deformity?		
4	Are you scheduled for lumbar spine surgery at Virtua Memorial Hospital		
	in the next 30 days?		
5	Are you willing to participate in the study and comply with the study		
	protocol?		

Exclusion criteria

#	Question	Feet	Inches
1	What is your current height?		
2	2 What is your current weight?		
		Yes	No
3	Have you ever been diagnosed with a mental health conditions such as anxiety or depression?		
4	Are you currently taking medication for depression, anxiety, or any other mental health condition (e.g. Prozac, Xanax, Ativan, Zoloft)?		
5	Have you ever been treated for alcohol, recreational drug, or narcotic medication abuse?		
6	Have you ever had an allergic reaction to any type of local anesthetic such as lidocaine, procaine, or Marcaine®?		
7	Have you ever had spinal fusion surgery (e.g. rods, screws, cages, implants) before?		
8	Have you been taking opioid analgesics (also known as narcotics) such as Vicodin, Percocet, or OxyContin for more than 30 days?		
	Females only:	Yes	No
9	If you are female are you currently pregnant, or do you plan on becoming pregnant before your surgery?		

Pain diagram

Instructions

Please indicate where you currently have pain in your body.

Please use the marks below to indicate each type of symptom you may have.

ACHE	NUMBNESS	PINS & NEEDLES	BURNING	STABBING
$\land \land \land \land$	0000	====	XXXX	////
$\land \land \land \land$	0000	====	XXXX	////

Pain medication questionnaire

Instructions

Please indicate if you have taken any of the following medications for pain in the past month:

Brand name	Generic name	Yes	No
Actiq	Fentanyl transmucosal		
Advil	Ibuprofen		
Aleve	Naproxen		
Avinza	Morphine extended-release		
Bayer	Aspirin		
Butrans	Buprenorphine transdermal		
Celebrex	Celecoxib		
Codeine	Codeine		
Darvocet	Dextropropoxyphene		
Darvon	Propoxyphene		
Demerol	Meperidine		
Dilaudid	Hydromorphone		
Dolophine	Methadone		
Duragesic	Fentanyl transdermal		
Embeda	Morphine / naltrexone extended release		
Exalgo	Hydromorphone extended release		
Excedrin	Acetaminophen / aspirin / caffeine		
Fioricet	Butalbital / acetaminophen / caffeine		

Fiorinal	Butalbital / aspirin / caffeine	
Flexeril	Cyclobenzaprine	
Kadian	Morphine extended-release	
Levo-Dromoran	Levorphanol	
Lorcet	Hydrocodone / acetaminophen	
Lortab	Hydrocodone / acetaminophen	
Lyrica	Pregabalin	
Morphine	Morphine	
MS Contin	Morphine controlled release	
Neurontin	Gabapentin	
Norco	Hydrocodone / acetaminophen	
Nucynta ER	Tapentadol extended-release	
Opana	Oxymorphone	
Opana ER	Oxymorphone extended-release	
OxyContin	Oxycodone	
OxyContin CR	Oxycodone controlled release	
Percocet	Oxycodone / acetaminophen	
Robaxin	Methocarbamol	
Skelaxin	Metaxalone	
Soma	Carisoprodol	
Toradol	Ketorolac	
Tylenol	Acetaminophen	
Tylenol #3	Acetaminophen / codeine	
Ultracet	Tramadol / acetaminophen	
Ultram	Tramadol	
Vicodin	Hydrocodone / acetaminophen	
Voltaren	Diclofenac	

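### No preoperative pain intensity score is planned and mean pain is compared by unadjusted ANOVA, so the primary analysis forgoes precision that one baseline question could supply

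*Combined protocol and SAP*

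**What the plan says.** The Background and Statement of Context lists, among the reasons for severe postsurgical pain after spine surgery, "the existence of preoperative pain, and opioid-induced hyperalgesia (OIH) that may occur with pre-operative opioid use".

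Appendix 1 holds the only baseline pain items in the plan. The pain diagram says "Please indicate where you currently have pain in your body" and asks for marks showing the type of symptom. A checklist records, yes or no, which pain medicines were taken in the past month. One further yes/no item asks about opioid use for more than 30 days. No item in the text asks for pain intensity.

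Study Methodology defines the endpoint: "The primary outcome in this study will be the mean postoperative pain score derived from the pain scores recorded by the nursing staff", on a 0-10 scale over the whole hospital stay. The sample size takes a "target reduction in mean overall postoperative pain scores of 1 point on the VAS". For the spread of the score it uses "our anticipated variance of 2". The method is a one-way ANOVA without covariate; at "statistical power of 80% and significance level of 0.05" it gives 40 per group as the minimum. Enrolment is set at 45 per group.

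For the analysis, "Means will be compared among all the three arms using analysis of variance". The only adjustment mentioned is a logistic regression for confounding, with no covariates named.

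**The concern.** A pain score taken before treatment is a natural covariate for a pain score taken after it. If the two are correlated, adjustment removes part of the between-patient variation from the error term and narrows the comparison of arms at the same sample size. The plan points to preoperative pain as a contributor to the outcome, yet plans no measure of its intensity and no model that could use one. Logistic regression does not fill the gap, because it does not fit a continuous mean pain score.

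What is at stake is power and interval width for the primary comparison. A baseline score that is not taken before surgery cannot be recovered reliably afterwards, so the choice has to be made before enrolment.

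**Working it through.** **Inputs from Study Methodology.** Three arms; difference δ = 1 point; variance σ² = 2; alpha 0.05; power 80%; n = 40 evaluable and 45 enrolled per group; one-way ANOVA without covariate.

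**Assumed input.** r, the correlation between preoperative pain intensity and mean postoperative pain. The documents give none, so a range is shown.

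**Step 1: reproduce the plan's figure.** Put two means 1 point apart and the third midway: 0, 0.5, 1. The squared deviations from the grand mean sum to 0.25 + 0 + 0.25 = 0.5. The noncentrality is λ = n × 0.5/σ² = 40 × 0.5/2 = 10, with 2 and 3 × 40 − 3 = 117 degrees of freedom. Noncentral F power is 80.5% at n = 40 and 79.4% at n = 39, so the stated 40 is exactly the minimum. Two other readings do not give 40:

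- A standard deviation of 2 in place of a variance of 2 needs 79 per group.
- One arm differing by 1 point from two equal arms needs 30.

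**Step 2: add the covariate.** ANCOVA reduces the residual variance to 2(1 − r²), multiplies the standard error by √(1 − r²), and costs one error degree of freedom (116 at n = 40). The noncentrality becomes λ = 10/(1 − r²) at n = 40.

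| Assumed r | Residual variance | SE ratio | Power, 40 per group | Power, 45 per group | n per group for 80% |
|---|---|---|---|---|---|
| unadjusted | 2.00 | 1.000 | 80.5% | 85.2% | 40 |
| 0.1 | 1.98 | 0.995 | 80.9% | 85.6% | 40 |
| 0.2 | 1.92 | 0.980 | 82.1% | 86.7% | 39 |
| 0.3 | 1.82 | 0.954 | 84.2% | 88.5% | 37 |
| 0.4 | 1.68 | 0.917 | 87.2% | 91.0% | 34 |
| 0.5 | 1.50 | 0.866 | 90.8% | 93.9% | 30 |

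**Step 3: put the gain in other units.** In information terms, adjustment at r = 0.4 is worth 40/(1 − 0.16) = 47.6, or about 48 unadjusted patients per group. At r = 0.2 it is worth 40/(1 − 0.04) = 41.7. The approximate 95% half-width for a pairwise difference is 1.96 × √(2 × 2/40) = 0.62 points unadjusted, and 0.62 × 0.954 = 0.59 points at r = 0.3.

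**The case against.** The strongest reply is that nothing in the plan is wrong. Randomisation keeps the unadjusted comparison unbiased, the sample size reproduces without a covariate, and 45 per group are to be enrolled. All of that stands.

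Four stronger readings might be inferred, and the documents support none of them:

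- **Chance imbalance in baseline pain biases the result.** It does not. Allocation by die roll can leave the arms unequal, but that variation is already within the variance of 2 and the ANOVA error rate. Adjustment reduces random error.
- **The trial is underpowered for want of the covariate.** Step 1 shows 80.5% power on the plan's own assumptions.
- **The Background shows that intensity predicts who will hurt more.** It explains why spine surgery as a class is painful. It mentions the existence of preoperative pain and gives no correlation. Most qualifying indications are painful conditions, and averaging scores over a stay with rescue opioids available may compress differences between patients. A low r is therefore possible, which is why the table starts at 0.1.
- **No preoperative pain score will exist anywhere.** Routine charts may hold one, and the pain diagram's figure is missing from the text available. What can be said is that the plan describes no intensity item and no use of one.

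It is also fair that other candidate covariates (number of levels, fusion, opioid use beyond 30 days) need no new data, and that the gain from baseline pain beyond these could be smaller than the table shows. The plan names none of them as a covariate either.

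**Conclusion.** The point holds as forgone precision. The plan records no preoperative pain intensity for use in the analysis, and its primary comparison is unadjusted. The gain from changing this is under 2 power points at r of 0.2 or less, and about 4 to 10 points at r from 0.3 to 0.5, with 40 per group. These figures rest on the plan's variance of 2 and 1-point difference, the midpoint pattern of means that reproduces its sample size, a linear relation between baseline and outcome, and an r that the documents do not supply. Severity is low: a cheap improvement that does not call the planned analysis or the sample size into question.

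**What to change.** 1. Record one 0-10 pain score on the day of surgery, before the die roll, so that it cannot be affected by allocation. Name this score as the covariate.
2. Add the same 0-10 item beside the pain diagram in Appendix 1, to be used only when the day-of-surgery score is missing. The form allows surgery up to 30 days after screening, so the earlier score is the weaker choice. If both are missing, impute the overall mean across arms.
3. Use the scale of the primary outcome. That scale must first be settled: Study Questions/Objectives and Hypothesis says Wong-Baker faces, whereas Study Methodology says visual analog scale.
4. Prespecify ANCOVA with arm and this single baseline score as the primary analysis, in place of the unadjusted ANOVA. Leave the sample size as it is, because r is unknown.

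The cost is one short question, asked at screening and again on the day of surgery, one error degree of freedom, and occasional missing baseline values covered by the rule above. At 40 per group the lost degree of freedom has almost no effect on power, so little is lost if r proves small.
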